5. TREATMENT PLAN

Patients will be screened for eligibility within 7 days of day 1. Starting dose will be 3 mg daily for days 1-21 of every 28-day cycle. Concomitant corticosteroid administration is not allowed for treatment of underlying malignancy (ALL) but is allowed for treatment emergent medical conditions that would ordinarily require corticosteroids, e.g., diffuse alveolar hemorrhage or severe treatment emergent dermatological conditions.

Timing of treatment should be such that pretreatment and day 8 marrows can be shipped on Monday-Thursday as described in Section 9.2.

All patients will receive one dose of clinically indicated intrathecal (IT) chemotherapy prophylactically within one week of starting study treatment. For patients with malignant CSF and due to poor penetration of CSF by MLN0128 (TAK-228), patients can be treated with IT methotrexate or cytarabine per standard practice of participating institution. At the time of IT1 chemotherapy performed prior to study treatment and any clinically indicated subsequent IT chemotherapy performed during the study, up to a 2 mL sample of CSF will be collected for MLN0128 (TAK-228) pharmacokinetics if possible.

Responders (CR/CRI/PR/MLFS) to therapy at any time can proceed to consolidation therapy at 3 mg orally daily for 21-days every 28-day cycle until disease progression and as long as they are tolerating MLN0128 (TAK-228). Responders may go off study and proceed to stem cell transplantation if candidate and donor are available at any time.

Patients who achieve a PR with MLN0128 (TAK-228) will, by definition, have normalization of

platelet and neutrophil counts despite persistent identifiable blasts in the bone marrow. It is unclear how long they might respond to MLN0128 (TAK-228) and whether they are at risk of rapid progression while on this agent. Accordingly, all patients in PR after two cycles will be discussed with the study PI and CTEP monitor in a timely fashion to determine on a case by case basis whether continued treatment at same dose, escalation to a higher dose (per Section 6.0) or removal from study for an alternative regimen with a well described response rate in relapsed/refractory ALL is the best course of action

Non-responders and PR after 2 cycles of therapy (with no evidence of significant drug-related toxicity) could proceed to dose level +1 (4 mg orally daily for 21 days every 28-day cycle). Non-responders and PR after 2 additional cycles (with no evidence of significant drug-related toxicity) of dose escalation (end of cycle 4) could proceed to dose level +2 (4 mg orally daily for 28 days every 28-day cycle). Non-responders after 2 cycles (end of cycle 6), will be taken off study.

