6. DOSING DELAYS/DOSE MODIFICATIONS

Dose de-escalation will be pursued if patients develop a significant related AE as below.

Dose escalation could be chosen if patients fail to show a response (CR/CRi/ MLFS) and show no evidence of drug-related toxicity. Dose escalation or re-escalation will be done after a dose has been tolerated for 2 cycles.

Dose delays are allowed for a maximum of 1 cycle if patient develops a related toxicity and 2 months if unrelated toxicity (disease related for example).

Dose Level	MLN0128 (TAK-228) Dose
-2	2 mg orally Monday-Friday, weeks 1 - 3 of each 28-day cycle
-1	2 mg orally days 1 - 21
0	3 mg orally days 1 - 21
+1	4 mg orally days 1 - 21
+2	4 mg orally days 1 - 28

Note: All treatment modifications must be expressed as a specific dose or amount rather than as a percentage of the starting or previous dose.

Nausea	Management/Next Dose for MLN0128 (TAK-228)
≤ Grade 1	No change in dose
Grade 2	Hold until ≤ Grade 1. Resume at same dose level.
Grade 3	If experienced for ≤ 72 hours, hold MLN0128 (TAK-228) until ≤ Grade 1, then resume MLN0128 (TAK-228) without dose modification. If experienced for > 72 hours despite optimal therapy, hold MLN0128 (TAK-228) until ≤ Grade 1, then resume treatment with the dose of MLN0128 (TAK-228) reduced by 1 level.
Grade 4	Off protocol therapy

*Patients requiring a delay of > 4 weeks if related to MLN0128 (TAK-228) should go off protocol therapy.

Vomiting	Management/Next Dose for MLN0128 (TAK-228)
≤ Grade 1	No change in dose
Grade 2	Hold until ≤ Grade 1. Resume at same dose level.
Grade 3	If experienced for ≤ 72 hours, hold MLN0128 (TAK-228) until ≤ Grade 1, then resume MLN0128 (TAK-228) without dose modification. If experienced for > 72 hours despite optimal therapy, hold MLN0128 (TAK-228) until ≤ Grade 1, then resume treatment with the dose of MLN0128 (TAK-228) reduced by 1 level.
Grade 4	Off protocol therapy

*Patients requiring a delay of > 4 weeks if related to MLN0128 (TAK-228) should go off protocol therapy.

Diarrhea	Management/Next Dose for MLN0128 (TAK-228)
≤ Grade 1	No change in dose
Grade 2	Hold until ≤ Grade 1. Resume at same dose level.
Grade 3	Hold* until < Grade 2. Resume at one dose level lower
Grade 4	Off protocol therapy
*Patients requiring a delay of > 4 weeks if related to MLN0128 (TAK-228) should go off protocol therapy.	
**Patients requiring > two dose reductions should go off protocol therapy.	

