13.5 Safety Analysis

13.5.1 A safety analysis will be performed after the first 6 patients have been accrued to the study on dose 0 (3 mg, orally days 1-21). If 2 or more of the first 6 patients experience a dose-limiting toxicity (DLT) as defined below, then 6 patients will be enrolled on dose -1 (2 mg, orally days 1-21). If 2 or more of the second 6 patients experience DLT, then the study will be terminated.

13.5.2 Toxicity will be measured per NCI-CTCAE version 4. DLT is defined as an adverse event possibly, probably, or definitely related to study treatment that meets one of the following:

- Any grade 4 drug-related non-hematological toxicity
- Any grade 3 drug-related non-hematological toxicity that does not resolve to < grade 3 within 3 days, with the following exceptions:
 - Grade 3 Bilirubin, AST, ALT, Alkaline phosphatase will be considered DLT only if it does not recover to <grade 3 within 7 days
- Myelosuppression: hypoplasia (bone marrow cellularity <10%) >50 days

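### Section 5 names 3 mg as the only consolidation dose, which conflicts with the Section 6 reductions, the 13.5.1 de-escalation and the handling of partial responders

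*Combined protocol and SAP*

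**What the plan says.** Section 5 sets the starting dose without condition: "Starting dose will be 3 mg daily for days 1-21 of every 28-day cycle". At any time, patients with CR, CRi, PR or MLFS "can proceed to consolidation therapy at 3 mg orally daily for 21-days every 28-day cycle until disease progression". The sentence makes this conditional on the drug being tolerated. No alternative consolidation dose is given, and the sentence does not refer to the patient's current, reduced or safe dose.

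Other current text puts patients on other doses:

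- **Section 6.** "Dose de-escalation will be pursued if patients develop a significant related AE as below". Level -1 is 2 mg on days 1-21, and level -2 is 2 mg Monday to Friday in weeks 1-3. Escalation or re-escalation follows two tolerated cycles.
- **Section 13.5.1.** If 2 or more of the first 6 patients at 3 mg have a DLT, "then 6 patients will be enrolled on dose -1 (2 mg, orally days 1-21").
- **Section 5, escalation.** "Non-responders and PR after 2 cycles of therapy (with no evidence of significant drug-related toxicity) could proceed to dose level +1", which is 4 mg on days 1-21. Level +2 is 4 mg on days 1-28.
- **Section 5, partial responders.** After two cycles the study PI and CTEP monitor decide case by case "whether continued treatment at same dose, escalation to a higher dose (per Section 6.0") or removal from study is best.

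Section 13.1.2.1 counts response over all cycles. Section 13.1.2.3 summarizes patients not treated at the safe dose separately and leaves them out of the final decision rule.

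**The concern.** A responder need not be at 3 mg when the response is recorded. Read literally, the consolidation sentence sends a patient whose dose was reduced for toxicity, or who was enrolled at 2 mg because the safety analysis rejected 3 mg, to 3 mg at the moment of response. No text says whether Section 5 or Section 6 then governs, so sites could treat similar patients differently.

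Two things are at stake. The first is safety: re-exposure to a dose that the plan's own rules had reduced or rejected. The second is interpretation. If 2 mg became the safe dose, a PR or MLFS that turned into CR or CRi during consolidation at 3 mg would count as a success although it was completed at another dose. CR/CRi duration (13.4.2) would also run across a dose change made at response.

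**Working it through.** **The plan's own figures.** The concern does not rest on the design table in 13.1.3, but I checked the table first. With 11 patients at the interim (stop at 1 or fewer successes) and 26 in total (5 or more needed), the probability of declaring success is the sum over x = 2 to 11 of P(X1 = x | 11, p) × P(X2 ≥ max(0, 5 − x) | 15, p).

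- At p = 0.10 this is 0.0865 (stated 0.09). At p = 0.30 it is 0.8516 (stated 0.85).
- The probability of stopping at the interim is 0.697 at p = 0.10 (stated 0.70) and 0.113 at p = 0.30 (stated 0.11).
- Maximum accrual is 26 + 6 + 3 = 35, as stated in 13.2.1.

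The table reproduces.

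**Passages side by side, by dose at response.**

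1. *Level 0.* Consolidation at 3 mg is the dose already being taken, so there is no conflict.
2. *Level -1 or -2 after an individual reduction.* Section 5 names 3 mg on response. Section 6 lets the dose go back up only after two tolerated cycles. A response recorded before that point meets two incompatible instructions. Section 6 expects some responders to be below 3 mg: its cytopenia reductions apply only in remission, and it allows retreatment at a reduced level after grade 4 non-hematological toxicity where there is clinical benefit.
3. *Dose -1 cohort under 13.5.1.* Nothing in Section 5 changes when enrolment moves to 2 mg. The starting and consolidation doses remain 3 mg, and the next step for non-responders and PR after two cycles is still that they "could proceed to dose level +1 (4 mg orally daily for 21 days every 28-day cycle"). Sections 13.1.2.1 and 13.1.2.3 do not say how a response first reached after a move off the safe dose is handled.
4. *PR at any level.* Section 5 lists PR among the responses that lead to 3 mg consolidation, and 5.3 also counts PR as response. After two cycles Section 5 sends the same patients to a choice of same dose, higher dose or removal. The Section 6 escalation sentence lists only CR, CRi and MLFS as response. A PR patient is therefore a responder in one place and a candidate for escalation in another.
5. *CR, CRi or MLFS at +1 or +2.* No rule requires the escalated dose to be kept, so 3 mg is an unexplained step down.

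**How likely the 13.5.1 switch is.** With true DLT rate q at 3 mg:

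P(2 or more in 6) = 1 − (1 − q)^6 − 6q(1 − q)^5

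- q = 1/11 (1 DLT in 11 patients at 3 mg daily, 2.2.7): 1 − 0.564 − 0.339 = 0.097
- q = 0.20 (assumption): 1 − 0.2621 − 0.3932 = 0.345 to three decimals (0.3446, or 0.34)
- q = 0.33 (assumption): 1 − 0.0905 − 0.2673 = 0.642

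**The case against.** Section 5 is permissive: responders can proceed, and only while tolerating the drug. Section 5.1.1 points to Section 6 for dose modifications, and the Section 6 cytopenia table operates in remission. A fair reader may conclude that Section 5 states the level-0 base case and Section 6 modifies it. Section 6 also foresees going back up, so a reduced responder who has tolerated two cycles would not breach it by returning to 3 mg. The PR text can be read as a sequence, with consolidation first and the case-by-case decision after cycle 2. The over-accrual text (13.1.2.7) speaks of accrual at the safe dose, and 13.2.1 adds 6 patients if the initial cohort has undue toxicity. Both suggest that the decision set is defined by enrolment dose.

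Much of this stands. A reader might infer that 3 mg is imposed on every responder, or that any dose change creates a contradiction. The documents do not support either: the wording is conditional, and a reduction made during consolidation simply follows Section 6. A reader might also infer that escalated responders are returned to a dose that had failed. PR patients can be escalated too, and PR counts as response in Section 5 and in 5.3.

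What remains is narrower. Tolerating a reduced dose does not show that 3 mg is tolerated, and the tolerability clause offers no other dose. Section 5.1.1 does not say that Section 6 overrides the stated consolidation dose. Section 6 has no rule for a cohort switch under 13.5.1. Reading the PR text as a sequence does not settle the dose for a PR patient who is no longer at level 0. Defining the decision set by enrolment dose would settle membership, but not whether a CR reached at 3 mg counts as a success for 2 mg.

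**Conclusion.** The concern holds as an internal inconsistency in three places: responders already reduced under Section 6 who have not met the two-cycle condition, patients enrolled at dose -1 under 13.5.1, and partial responders. For CR, CRi or MLFS at +1 or +2 there is a gap in explanation, not a contradiction.

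The first and third conflicts need no probability, and the documents give no reduction or response rates from which to count the patients affected. The second arises only if 13.5.1 is triggered. That probability is about 0.10 at the only DLT rate the documents report for 3 mg daily, and 0.34 to 0.64 over assumed rates of 20% to 33%. A reader might take the higher values as expected frequencies. They are not: the true rate on this schedule in ALL is unknown, and 1 in 11 is itself imprecise.

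A reader might also infer that the error rates are wrong. They reproduce and are unaffected. CR/CRi duration is a descriptive Kaplan-Meier secondary endpoint with no test, so the effect there is on interpretation only. The point is worth correcting because a site that follows Section 5 literally would act against Section 6 or 13.5.1.

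**What to change.** The sponsor should reconcile the starting-dose, consolidation, PR and escalation text in Section 5 with Section 6, 13.1.2.3 and 13.5.1. The amended text should state which passage governs:

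- dose during consolidation for a patient whose dose has already been changed;
- starting, consolidation and escalation doses after a de-escalation under 13.5.1;
- dose for a partial responder, with PR classed the same way in Sections 5 and 6.

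Section 13.1.2.3 should then say at what time a patient's dose is judged for membership of the decision set, and how a response first reached after a dose change is counted.

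No dose or clinical rule is proposed here; that choice is the sponsor's. The cost is a wording amendment, with no change to sample size, decision boundaries or data collection.

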13.6.1 Adverse Event Stopping Rule

The stopping rules specified below are based on the knowledge available at study development. We note that the Adverse Event Stopping Rule may be adjusted in the event of either (1) the study re-opening to accrual or (2) at any time during the conduct of the trial and in consideration of newly acquired information regarding the adverse event profile of the treatment(s) under investigation. The study team may choose to suspend accrual because of unexpected adverse event profiles that have not crossed the specified rule below.

Accrual will be temporarily suspended to this study if at any time we observe events considered at least possibly related to study treatment (i.e. an adverse event with attribute specified as “possible”, “probable”, or “definite”) that satisfy any of the following:

- If 3 or more out of the first 12 treated patients experience grade 4 non-hematological toxicities at least possibly related to treatment excluding fatigue, fever, infection, and lab abnormalities (hyper- or hypokalemia, hypocalcemia, hyperuricemia, hypophosphatemia) that resolve within 7 days without jeopardizing patient safety.
- If after the first 12 patients have been treated, 25% of patients experience grade 4 non-hematologic toxicities at least possibly related to treatment excluding fatigue, fever, infection, and lab abnormalities (hyper- or hypokalemia, hypocalcemia, hyperuricemia, hypophosphatemia) that resolve within 7 days without jeopardizing patient safety.

We note that we will review grade 4 and 5 adverse events deemed “unrelated” or “unlikely to be related”, to verify their attribution and to monitor the emergence of a previously unrecognized treatment-related adverse event.

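### If the DLT rule in 13.5.1 moves entry from 3 mg to 2 mg, the consolidation and escalation doses in Sections 5 and 6 stay as written for a 3 mg start

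*Combined protocol and SAP*

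**What the plan says.** Section 5 is built on one entry dose: "Starting dose will be 3 mg daily for days 1-21 of every 28-day cycle". Three later provisions set what follows.

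- **Consolidation (Section 5).** Responders, at any time, "can proceed to consolidation therapy at 3 mg orally daily for 21-days every 28-day cycle until disease progression", provided they tolerate the drug.
- **Escalation (Section 5).** After 2 cycles without significant drug-related toxicity, non-responders and partial responders "could proceed to dose level +1 (4 mg orally daily for 21 days every 28-day cycle". After 2 more cycles they "could proceed to dose level +2 (4 mg orally daily for 28 days every 28-day cycle".
- **Escalation (Section 6).** "Dose escalation or re-escalation will be done after a dose has been tolerated for 2 cycles". It is offered to patients without CR, CRi or MLFS and without drug-related toxicity. In the dose table, level 0 (3 mg) lies directly above level -1 (2 mg).

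Section 13.5.1 gives the cohort rule. If 2 or more of the first 6 patients at 3 mg have a DLT, "then 6 patients will be enrolled on dose -1 (2 mg, orally days 1-21". It says nothing about consolidation or escalation.

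**The concern.** Section 13.5.1 changes the entry dose and nothing else. A patient who starts at 2 mg because 3 mg produced too many DLTs is still covered by a consolidation rule that names 3 mg, a first escalation step that names 4 mg, and a dose table that would make that step 3 mg. These give different answers for the same patient, and none depends on the outcome of the safety cohort.

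At stake is patient safety in a contingency that the protocol itself foresees. The conditions that remain are individual. Two tolerated cycles at 2 mg show tolerance of 2 mg, not of 3 mg or 4 mg. Consolidation has the lightest condition: no two-cycle wait, and no required case discussion for patients in CR, CRi or MLFS.

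The trial-wide rule in 13.6.1 would not necessarily catch the same events. It suspends accrual "If 3 or more out of the first 12 treated patients experience grade 4 non-hematological toxicities at least possibly related to treatment", with some exclusions, and continues after 12 patients at 25%. A DLT under 13.5.2 also includes "Any grade 3 drug-related non-hematological toxicity that does not resolve to < grade 3 within 3 days". Grade 3 events of the kind that closed entry at 3 mg would therefore not count, and suspending accrual does not stop dose steps in patients already on treatment.

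**Working it through.** **1. The provisions side by side, for a 2 mg starter after 13.5.1 has triggered**

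| Situation | Section 5 | Section 6 | Tied to 13.5.1? |
|---|---|---|---|
| Response at any time | Consolidation at 3 mg, if tolerated | No escalation offered to CR/CRi/MLFS | No |
| No response or PR after 2 cycles | 4 mg, days 1-21 (+1) | One level up: 3 mg, days 1-21 (0) | No |
| No response or PR after 2 further cycles | 4 mg, days 1-28 (+2) | One level up from the current dose | No |

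The only other text on the safe dose level, 13.1.2.3, decides who enters the primary analysis. It does not limit dosing.

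**2. The plan's own design figures**

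Inputs (13.1.2.4 to 13.1.3): stop if at most 1 success in 11; positive if at least 5 in 26; null rate 10%, target rate 30%.

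- P(early stop) = P(X ≤ 1 | n = 11, p): 0.697 at 10% and 0.113 at 30% (stated 0.70 and 0.11).
- P(positive) = sum over k = 2 to 11 of P(X₁ = k | 11, p) × P(X₂ ≥ 5 − k | 15, p): 0.0865 at 10% and 0.852 at 30% (stated 0.09 and 0.85).
- Maximum accrual: 26 + 6 + 3 = 35, as in 13.2.1.

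These depend on the response rate and the cut-offs, not on the dose steps, so the change proposed here alters none of them.

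**3. How likely the branch is**

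P(trigger) = P(X ≥ 2 | n = 6, q) = 1 − (1 − q)⁶ − 6q(1 − q)⁵.

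The one documented rate for milled 3 mg daily is 1 DLT in 11 (Section 2.2.7), exact 95% CI 0.2% to 41%.

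| DLT rate q | Basis | P(trigger) |
|---|---|---|
| 5% | assumed | 0.033 |
| 1/11 = 9.1% | Section 2.2.7 | 1 − 0.564 − 0.339 = 0.097 |
| 20% | assumed | 1 − 0.262 − 0.393 = 0.345 |
| 30% | assumed | 0.580 |

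The one earlier DLT was decreased platelets. Under 13.5.2 the only haematological DLT is marrow hypoplasia lasting more than 50 days, so on this trial's definition the earlier record may be 0/11, which would lower the probability. It does not exclude a higher rate: the one-sided 95% upper bound for 0/11 is 1 − 0.05^(1/11) = 0.238, where P(trigger) = 0.438.

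**4. What is known about 4 mg**

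Section 2.2.7 reports DLTs in 3 of 6 patients at milled 4 mg daily, exact 95% CI 12% to 88%. That dose and schedule match level +2. Level +1 has a week off in each cycle, and escalated patients would already have tolerated earlier cycles.

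**The case against.** The strongest reply is that the protocol deliberately separates the population entry dose from individual titration. Knowing of 3 DLTs in 6 patients at 4 mg, and with 3 mg as the recommended phase 2 dose, it still lets tolerant non-responders go from 3 mg to 4 mg. Section 13.5.1 governs enrolment and does not itself declare 3 mg forbidden. In a disease with a cited 3-month median survival, allowing such a patient one step up is a defensible benefit-risk choice. This stands in part, and it is why a total ban on a step from 2 to 3 mg would go too far.

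Three stronger readings are tempting but not supported.

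- **That the plan sends 2 mg starters straight to 4 mg.** Section 5 names 4 mg, but in a passage that assumes a 3 mg start, and for partial responders it refers escalation to Section 6, where 3 mg comes next. The documents leave the step unresolved.
- **That responders doing well on 2 mg must be raised to 3 mg.** The wording is permissive and conditional on tolerance, Section 6 does not offer escalation to patients in CR, CRi or MLFS, and the 3 mg may simply restate the starting dose. Taken literally it would also return to 3 mg a 3 mg starter who had been reduced for toxicity, which is strained. Still, 3 mg is the only consolidation dose named.
- **That week-8 survival caps the number exposed by any route.** With exponential survival and a 3-month median, 0.5^(56/91.3) × 26 = 17 patients are alive at week 8. That could bound only the escalation routes. Consolidation is open at any time, and at week 4 the same assumptions give 0.5^(28/91.3) × 26 = 21. Both figures assume full accrual of 26, although the interim rule stops the trial with probability 0.70 at a 10% response rate. No bound for all routes follows.

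Other safeguards are real: toxicity-based holds and reductions, the case discussion for partial responders after two cycles, discretionary suspension of accrual, an adjustable stopping rule, and DSMB review at least twice a year. They act on individuals, on accrual or at discretion. None states the dose for a 2 mg starter. The branch is also unlikely on the documented data, and the earlier 3 mg data come from daily dosing, not 21 days in 28.

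**Conclusion.** The gap is real and conditional. Once 13.5.1 has moved entry to 2 mg, Sections 5 and 6 still name 3 mg for consolidation and either 4 mg or 3 mg for the first escalation, under individual conditions only. The text therefore permits, without requiring, a dose at or above the one at which entry was closed.

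It arises with probability 0.10 if the true DLT rate equals the earlier 1/11, possibly less because of how that DLT was classified, and 0.34 if the rate is 20%, which is an assumption. These figures treat the 6 patients as independent with a common rate. The number of patients affected cannot be bounded usefully from the documents.

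A reader might infer that the efficacy decision is compromised. It is not: the stated alpha, power and stopping probabilities reproduce, and neither they nor the sample size depends on this wording. The point concerns safety and clarity of dosing. It is worth correcting because sites should not have to infer the rules for a contingency that the protocol wrote itself.

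**What to change.** Add to Sections 5 and 6 a paragraph that applies once 13.5.1 has moved entry to 2 mg:

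- Consolidation is given at the declared safe dose (2 mg), or at the patient's current dose if that has been reduced further.
- The fixed +1 and +2 steps (4 mg) no longer apply.
- By default, no patient is escalated or re-escalated to 3 mg or above.
- First-cohort patients who are tolerating 3 mg may continue it, without escalation, if the study PI and the CTEP monitor agree.
- Any exception for a single step from 2 to 3 mg in a tolerant non-responder needs the same agreement.

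This needs no extra patients, visits or procedures and leaves the decision rules unchanged. The cost is less optional escalation for non-responders in that branch.

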2.2.7 Milled MLN0128 (TAK-228) Drug Substance (DS, process B)

In order to allow more predictable absorption of MLN0128 (TAK-228) after oral administration and to allow scale-up manufacturing of MLN0128 (TAK-228) capsules, Millennium/Takeda developed a new milled formulation of the agent. The physical milling step during the granulation process controls particle size distribution of MLN0128 (TAK-228). In order to observe whether this milling step altered the safety and PK profile of MLN0128 (TAK-228), the company performed *in vivo* studies with PK analysis of milled MLN0128 (TAK-228). These studies indicated that the milled formulation may result in faster absorption with possibly higher maximum concentration (C_{max}), which could result in a different safety profile, compared to the previous unmilled API capsules. In rats, the mean AUC milled/unmilled was 2.97 ± 0.8, while in monkeys, it was 1.68 ± 0.86. The C_{max} ratios were 1.68 ± 0.86.

Takeda developed new MLN0128 (TAK-228) capsules containing milled active pharmaceutical ingredient (API) for clinical studies in 1 mg, 3 mg, and 5 mg strengths. Patients receiving the milled formulation were added onto ongoing studies C31001 and C31002, as well as a new study MLN0128-1004, to determine the PK parameters of milled and unmilled MLN0128 in patients administered single doses under both fasted and fed conditions, with various treatment cohorts including daily and weekly administration of milled MLN0128 (TAK-228).

The recommended dose of milled MLN0128 (TAK-228) was evaluated in 17 patients of

MLN0128-1004, with PK, safety, and tolerability assessed. Six patients were given a 4 mg QD dose of milled MLN0128 (TAK-228) and 3 patients had observed DLT (rash, appetite loss and fatigue). A dose of 3 mg QD was given to 11 patients with only 1 DLT (decreased platelets) observed. The 3 mg QD dose of MLN0128 (TAK-228) was declared the RP2D, and was generally well tolerated and demonstrating objective responses in patients.

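### Escalation to 4 mg levels +1 and +2 is offered under two different conditions, above a daily dose the protocol cites as the RP2D, and the DLT review names neither level

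*Combined protocol and SAP*

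**What the plan says.** **Escalation.** Treatment starts at 3 mg on days 1-21 of a 28-day cycle (level 0). Under Section 5, non-responders and PR patients after two cycles, if free of significant drug-related toxicity, "could proceed to dose level +1 (4 mg orally daily for 21 days every 28-day cycle". After two further cycles, under the same condition, they "could proceed to dose level +2 (4 mg orally daily for 28 days every 28-day cycle". The dose table in Section 6 lists both levels. Section 6 words the condition differently: patients must "show no evidence of drug-related toxicity", and "Dose escalation or re-escalation will be done after a dose has been tolerated for 2 cycles". Section 5.1.1, on agent administration, describes dosing on days 1-21 only.

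**Prior experience.** Section 2.2.7, on the milled formulation, states: "Six patients were given a 4 mg QD dose of milled MLN0128 (TAK-228) and 3 patients had observed DLT (rash, appetite loss and fatigue". It also states: "A dose of 3 mg QD was given to 11 patients with only 1 DLT (decreased platelets) observed". The 3 mg daily dose was then named the RP2D.

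**Safety rules.** Section 13.5 acts on the starting dose: "If 2 or more of the first 6 patients experience a dose-limiting toxicity (DLT", six more enter at level -1, and 2 or more DLTs among those six end the study. Section 13.6.1 suspends accrual when related grade 4 non-hematological toxicity occurs in 3 or more of the first 12 treated patients, or in 25% thereafter, "excluding fatigue, fever, infection, and lab abnormalities".

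**The concern.** Levels +1 and +2 are the only ones with a daily dose above the cited RP2D, and +2 appears to be the very schedule on which half of a six-patient cohort had DLT. Neither Section 5 nor Section 6 mentions that result or says why the levels are offered despite it. The protocol's one rule built on its DLT definition does not name them. The gate for reaching them also reads differently in two places, so two sites could treat the same patient differently. At stake are the safety of escalated patients and whether toxicity at these levels would be recognised as belonging to them.

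**Working it through.** **1. The plan's own figures.** No operating characteristics are given for any DLT rule, so there is none to reproduce. The efficacy table does reproduce. With stopping at 1 or fewer of 11 and success at 5 or more of 26, exact binomial calculation gives 0.0865 at a true rate of 10% and 0.8516 at 30% (stated 0.09 and 0.85). Interim stopping is 0.6974 and 0.1130 (stated 0.70 and 0.11). This point does not touch those figures.

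**2. Cited DLT rates (Section 2.2.7).** Exact 95% limits are the 0.025 quantile of Beta(x, n-x+1) and the 0.975 quantile of Beta(x+1, n-x).
- 4 mg daily: 3/6 = 50%, from Beta(3, 4) and Beta(4, 3): 11.8% to 88.2%.
- 3 mg daily: 1/11 = 9.1%, from Beta(1, 11) and Beta(2, 10): 0.2% to 41.3%.
- Fisher's exact two-sided p = 0.099.

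The contrast is large but imprecise.

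**3. How closely the levels match the cited cohort.** Drug per 28-day cycle:
- level 0: 3 × 21 = 63 mg
- level +1: 4 × 21 = 84 mg
- level +2: 4 × 28 = 112 mg (112/63 = 1.78 times level 0)

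Section 2.2.7 mentions no break in the daily schedule. If dosing there was continuous (an assumption), the 4 mg cohort received 4 × 28 = 112 mg per 28 days, the same as +2. Level +1 has a 7-day break, so 3/6 carries over to it less directly. Section 2.2.6 gives reversal of an uptake defect off drug as the reason for 21-of-28 dosing. Level +2 has no such interval, and no reason is given.

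**4. What each rule can see.**

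| | Section 13.5 | Section 13.6.1 |
|---|---|---|
| Levels | 0 and -1 named | all treated patients, pooled |
| Non-hematological events | related grade 4, and grade 3 not settling in 3 days (7 for liver tests) | related grade 4 only |
| Fatigue | counted if it meets the above | excluded |
| Limit | 2 or more of 6 | 3 or more of 12, then 25% |

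Fatigue is one of the three DLT terms reported at 4 mg. (The wording of 13.6.1 leaves open whether resolution within 7 days qualifies every excluded term or only the laboratory ones.) Pooling also dilutes. With 26 patients treated, 25% is 0.25 × 26 = 6.5. Six qualifying grade 4 events, all at +1 or +2, would be 6/26 = 23% and would not cross the limit unless three fell among the first 12 patients.

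Section 13.5 gives no observation window. It therefore does not say whether a DLT occurring after escalation in one of the first six patients would count.

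**5. The escalation condition.** A patient with minor drug-related toxicity meets Section 5, which bars only significant toxicity, and fails Section 6, which allows none. Section 6 then speaks of a dose having been tolerated, without defining the term.

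**The case against.** Several points on the other side are sound.

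- **Selection.** A patient reaching +2 has had two cycles at level 0 and two at +1 without significant related toxicity. The DLT rate in such patients may be below that of patients starting at 4 mg. A reader might apply the 2-of-6 limit to a 50% rate and get 1 - 0.5^6 - 6 × 0.5^6 = 57/64 = 0.89. That does not predict what escalated patients will experience: over the interval for 3/6 the probability runs from 0.15 to more than 0.999, and the documents give no rate for this group.
- **Like with like.** A reader might infer that 4 mg already fails the protocol's own limit. The cited study's DLT definition, grades and durations are not given, so 3 of 6 there is not shown to be 3 of 6 under Section 13.5. For level +1, the 84 mg per cycle equals 3 × 28 = 84 mg, the RP2D taken continuously.
- **How many escalate.** A reader might take everyone without CR/CRi as a candidate: 26 × 0.7 = 18 to 26 × 0.9 = 23 patients. This ignores MLFS, which counts as response, and losses to progression, toxicity and death before cycles 3 and 5. Section 2.1 cites a 3-month median survival. If survival were exponential with that median (an assumption), 26 × 0.5^(1.84/3) = 17 would be alive at 8 weeks and 26 × 0.5^(3.68/3) = 11 at 16 weeks, before the other losses.
- **Other safeguards.** A reader might conclude that nothing would act on toxicity at these levels. That is wrong. Section 13.6.1 covers all treated patients and lets the team suspend accrual without a crossed limit. The DSMB reviews safety at least twice a year (Section 13.6), Section 6 has patient-level hold, reduce and stop rules, and PR cases go to the study PI and the CTEP monitor (Section 5).
- **Not a contradiction in itself.** Escalation is optional, and an RP2D does not by itself bar escalation in an individual.

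These points limit the size of the concern. They do not supply a stated basis for the two levels, bring them into the DLT review, or settle which escalation condition applies.

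**Conclusion.** The concern stands in a limited form and should be fixed. Three things are documented. The protocol offers two levels above the cited RP2D daily dose without addressing its own report of 3/6 DLT (95% CI 12% to 88%) at 4 mg daily, against 1/11 at 3 mg. The only DLT-based review names neither level, and the pooled grade 4 rule is not a substitute. Sections 5 and 6 set conflicting escalation conditions, while Section 5.1.1 describes only days 1-21.

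Reading +2 as the same schedule as the cited cohort assumes continuous dosing there; for +1 the link is weaker. Neither the number of patients who will escalate nor their DLT rate can be estimated from the documents. They therefore do not support saying that most patients will reach these levels, that half of those will have DLT, or that 4 mg is unacceptable.

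**What to change.** The sponsor should reconcile Sections 2.2.7, 5, 5.1.1, 6 and 13.5:

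- use one escalation condition, worded identically in Sections 5 and 6, and make Section 5.1.1 consistent with the dose table;
- state the basis for offering +1 and +2 given the 3/6 result;
- state in Section 13.5 whether and how its DLT review applies to +1 and +2, including DLTs that occur after escalation;
- tabulate DLTs by dose level at the safety and DSMB reviews.

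Which levels and limits are acceptable is for the sponsor; none is proposed here. The cost is protocol wording and a tabulation from data already collected. Sample size and the efficacy decision rule are unchanged.
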